STUDY OBJECTIVES	
Primary objective:	To evaluate the overall joint status as detected by ultrasound (US) in haemophilia A and B patients treated with efmoroctocog alfa (rFVIIIfc) or eftrenonacog alfa (rFIXFc) prophylaxis over the 18-month study period.
Secondary objectives:	
 • To evaluate the joint status as detected by US in the Haemophilia Early Arthropathy Detection with Ultrasound (HEAD-US) specific items of hypertrophic synovium, cartilage and bone damage in haemophilia A and B patients treated with rFVIIIfc or rFIXFc prophylaxis over the 18-month study period • To evaluate the clinical joint status as detected by Hemophilia Joint Health Score (HJHS) in haemophilia A and B patients treated with rFVIIIfc or rFIXFc prophylaxis over the 18-month study period • To evaluate the presence, resolution, recurrence and new development of target joints in haemophilia A and B patients treated with rFVIIIfc or rFIXFc prophylaxis over 18 months • To describe the bleeding episodes in haemophilia A and B patients treated with rFVIIIfc or rFIXFc prophylaxis over the 18-month study period • To evaluate the quality of life in haemophilia A and B patients treated with rFVIIIfc or rFIXFc prophylaxis over the 18-month study period
Exploratory objectives – florio® HAEMO sub-study:	
 • Impact of florio HAEMO on patients' sense of protection and their physical activity level in haemophilia A and B patients treated with rFVIIIfc or rFIXFc prophylaxis • Explore adherence to prescribed treatment regimen in haemophilia A and B patients treated with rFVIIIfc or rFIXFc prophylaxis • Explore relationship between estimated FVIII and FIX levels and physical activity in haemophilia A and B patients treated with rFVIIIfc or rFIXFc prophylaxis • Explore timing of bleeding episodes in relation to estimated FVIII and FIX levels and physical activity in haemophilia A and B patients treated with rFVIIIfc or rFIXFc prophylaxis • Explore the use of florio HAEMO to characterise pain and well-being in haemophilia A and B patients treated with rFVIIIfc or rFIXFc prophylaxis
STUDY ENDPOINTS	
Primary endpoint:	
 • Change from baseline in total HEAD-US score up to month 18 (end of study - EOS).

Confidential

Page 6 of 56

Version 1.0 Final 15 November 2022

Sobi

Eftrenonacog alfa/Alprolix® - Efmorococog alfa/Elocta®

Clinical Study No: Sobi.HAEM89-007

Secondary endpoints:	
 Change from baseline in HEAD-US score for hypertrophic synovium at 6, 12 and 18 months Change from baseline in HEAD-US score for cartilage at 6, 12 and 18 months Change from baseline in HEAD-US score for bone at 6, 12 and 18 months Change from baseline in total HJHS at month 18 (EOS) Number and location of target joints at baseline, 6, 12 and 18 months Total Annualized bleeding rate (ABR), joint ABR, target joint ABR, traumatic/spontaneous ABR Patient-Reported Outcomes Measurement Information System (PROMIS) physical function/activity scores at baseline and 18 months PROMIS pain intensity and interference scores at baseline and 18 months IPAQ-SF scores at baseline and 18 months
Exploratory endpoints – florio HAEMO sub-study:	
 Results from questionnaire on impact of florio HAEMO tools on patients' sense of protection and their physical activity level florio HAEMO captured treatment adherence scores florio HAEMO captured estimated FVIII and FIX levels florio HAEMO captured physical activity type, duration and intensity florio HAEMO captured bleed data (timing, location, cause, treated/untreated) florio HAEMO captured FVIII/FIX administration data (time, dose) florio HAEMO captured pain data (time, location, cause, intensity) florio HAEMO captured well-being data
STUDY DESIGN AND METHODS	
Study design:	
This is a prospective, low-interventional, single-arm, multicentre study to describe the joint health over an 18-month period of prophylactic treatment with rFVIIIIfc or rFIXFc in patients with haemophilia A or haemophilia B in a real-world setting. Approximately 250 patients will be enrolled in the study. Around 80% of the patients are expected to have haemophilia A and around 20% haemophilia B.
 
Retrospective data from patient medical records will be collected for at least 6 months before enrolment in the study. From enrolment and throughout the study, patients will perform on-site study visits at 6-month intervals. Each patient is expected to actively participate in the study for 18 months (from baseline to EOS visit).
 
Joint health will be assessed with HEAD-US and HJHS scoring. Quality of life and physical activity will be assessed with Patient-reported outcomes (PROs). Patients will be on prophylactic treatment with rFVIIIIfc or rFIXFc according to usual clinical practice and the dosing guide in the respective Summary of Product Characteristics (SmPC). Choice of treatment will not be dictated by the study protocol.
 
6 months retrospective phase 18 months prospective low-interventional phase
 
rFVIIIIfc or rFIXFc Haemophilia A: rFVIIIIfc (~80%)
 
Non rFVIIIIfc or rFIXFc Haemophilia B: rFIXFc (~20%)
 
Baseline 6 months 12 months 18 months
 
Optional florio HAEMO sub-study

Confidential

Page 7 of 56

Version 1.0 Final 15 November 2022

Sobi

Eftrenonacog alfa/Alprolix® - Efmorocog alfa/Elocta®

Clinical Study No: Sobi.HAEM89-007

Number of patients planned:	Approximately 250. Around 80% of the patients are expected to have Haemophilia A and around 20% Haemophilia B.
Diagnosis and main criteria for inclusion:	
A patient must fulfill the following criteria in order to be included in the study:
 
 1. Age \geq 6 years 2. Diagnosis of haemophilia A or B 3. Having at least 6 months documented pre-study treatment data regarding treatment prescriptions and bleeding episodes prior to the baseline visit 4. Previous treatment for haemophilia A or B with any marketed recombinant and/or plasma-derived FVIII or FIX concentrate for at least 6 months 5. Start of prophylactic treatment with rFVIIIFc or rFIXFc prior to study enrolment or latest at the baseline visit, in accordance with local regulations 6. Signed and dated informed consent provided by the patient, or the patient's legally authorized representative for patients under the legal age. Assent should be obtained from paediatric patients in accordance with local regulations 
florio HAEMO sub-study
 
To be eligible for the florio HAEMO sub-study a patient should have used florio HAEMO (a CE marked medical device used in routine clinical practice) for at least 3 months and must agree to have data collected from the florio HAEMO app by providing a separate informed consent or assent.

Assessments:	
 • At each visit HEAD-US assessments will be performed. Information on pain, anti-inflammatory and anti-depressant medications will be recorded • At enrolment/baseline and EOS, PROs will be completed • At enrolment/baseline and EOS, HJHS will be assessed • For patients participating in the florio HAEMO sub-study a questionnaire on the impact of florio HAEMO on patients' sense of protection and their physical activity level will be administered when they enter the sub-study. Data from the florio HAEMO app will be collected 
Safety Assessments:
 
The following safety events should be collected:
 
 • Serious Adverse Events (SAEs) • Non-serious Adverse Events (AEs) assessed as causally related to treatment with rFVIIIFc or rFIXFc and considered unexpected • AEs of special interest: inhibitor development, thrombotic events and serious hypersensitivity reaction including anaphylactic reactions • AEs leading to premature discontinuation of rFVIIIFc or rFIXFc • Exposure during pregnancy, medication errors, misuse or abuse in relation to rFVIIIFc or rFIXFc 
Any AE suspected to be causally related to a medicinal product other than the studied Sobi product, and which does not result from a possible interaction with it, should be reported by the Investigator to the concerned authority via the national reporting system, or to the Marketing Authorization Holder of the suspected medicinal product.

Confidential

Page 8 of 56

Version 1.0 Final 15 November 2022

Sobi

Eftrenonacog alfa/Alprolix® - Efmoroctocog alfa/Elocta®

Clinical Study No: Sobi.HAEM89-007

Test product; dose and mode of administration:	N/A																							
Reference product; dose and mode of administration:	N/A																							
Auxiliary medicinal products:	N/A																							
Duration of treatment(s):	According to routine clinical practice																							
Determination of sample size:	
With a sample size of 250 patients (200 with Haemophilia A and 50 with Haemophilia B) assuming a standard deviation of 13, the mean change from baseline in Total HEAD-US score will be estimated with a level of accuracy that is lower than a clinically meaningful worsening of 2, e.g. a half width of 1.61.
 
  
 Confidence level	Standard deviation	n	Half width	
   
 95%	7	250	0.87	
 
 95%	10	250	1.25	
 
 95%	13	250	1.61	
 
 95%	13	200	1.80	
  
				Confidence level	Standard deviation	n	Half width	95%	7	250	0.87	95%	10	250	1.25	95%	13	250	1.61	95%	13	200	1.80
Confidence level	Standard deviation	n	Half width																					
95%	7	250	0.87																					
95%	10	250	1.25																					
95%	13	250	1.61																					
95%	13	200	1.80																					
Statistical methods:	
No formal hypothesis testing will be performed. Mean change from baseline will be estimated using a generalized linear mixed model with repeated measures, adjusted for clinically important covariates.
 
All continuous variables will be summarized with descriptive statistics including number of observations, mean, standard deviation, median, quartiles, minimum and maximum values. Categorical variables will be summarized in frequency tables including number of observed responses in each category as well as percentages.
 
Number of missing observations will also be displayed. No formal statistical hypothesis testing is planned.
 
Subgroups will be created to further explore the endpoints e.g. for age, severity of haemophilia, type of haemophilia, presence of joint disease at inclusion, and intensity of treatment.
																							

Sobi

Eftrenonacog alfa/Alprolix® - Efmorocog alfa/Elocta®

Clinical Study No: Sobi.HAEM89-007

2 Abbreviations and definition of terms

2.1 List of Abbreviations and definitions

Term	Definition
ABR	Annualized bleeding rate
AE	Adverse event
Bleeding episode	A bleeding episode starts from the first sign/symptom of bleeding as reported by the patient and ends no more than 72 hours after the last injection to treat the bleeding episode (1). Any subsequent bleeding at the same location and injections administered ≤ 72 hours from the previous injection will be considered as the same bleeding episode. Multiple bleeding locations treated with a single injection will also be considered a single bleeding episode. Any injection to treat the bleeding episode that is administered >72 hours after the preceding one will be considered the first injection to treat a new bleeding episode in the same location. Any injection used to treat subsequent bleeding at a different location will be considered a separate bleeding episode, regardless of the time from the last injection to treat a bleeding episode.
BU	Bethesda unit
CDISC	Clinical data interchange standards consortium
CRO	Contract research organization
(e)CRF	(electronic) Case report form
EOS	End of study
EDC	Electronic data capture
EU	European Union
FAS	Full analysis set
FIX	Factor IX
FVIII	Factor VIII
GCP	Good clinical practice
GPV	Global pharmacovigilance & patient safety
Haemophilia severity	Mild haemophilia: >5 IU/dL to <40 IU/dL endogenous factor VIII/IX

Sobi

Eftrenonacog alfa/Alprolix® - Efmoroctocog alfa/Elocta®

Clinical Study No: Sobi.HAEM89-007

Term	Definition
	Moderate haemophilia: 1 to 5 IU/dL endogenous factor VIII/IX Severe haemophilia: <1 IU/dL endogenous factor VIII/IX
HEAD-US	Haemophilia Early Arthropathy Detection with Ultrasound
HRQoL	Health-related quality of life
HJHS	Hemophilia Joint Health Score
ICH	International council for harmonisation
IEC	Independent ethics committee
IPAQ-SF	International Physical Activity Questionnaire - Short Form
Impaired joint	Any joint that has persistent functional or structural abnormalities, considered clinically relevant by the Investigator, with or without bleeding episodes.
Index joint	Ankle, knee, elbow (left and right)
Major surgery	Any surgical procedure (elective or emergent) that usually, but not always, involves general anesthesia and/or respiratory assistance, in which a major body cavity is penetrated and exposed, or a substantial impairment of physical or physiological functions is produced (e.g., laparotomy, thoracotomy, craniotomy, operation in joint, or dental extraction of any molar teeth or ≥ 3 nonmolar teeth).
Minor surgery	Any surgery that do not fall under the definition of Major surgery
MRI	Magnetic resonance imaging
NIH	National Institute of Health
PP	Per Protocol
PRO	Patient-reported outcome
PROMIS	Patient-Reported Outcomes Measurement Information System (PROMIS®)
rFVIIIFc	Efmoroctocog alfa (a recombinant FVIII Fc fusion protein, Elocta®)
rFIXFc	Eftrenonacog alfa (a recombinant FIX Fc fusion protein, Alprolix®)
ROM	Range of motion

Confidential

Page 11 of 56

Version 1.0 Final 15 November 2022

Sobi

Eftrenonacog alfa/Alprolix® - Efmorocog alfa/Elocta®

Clinical Study No: Sobi.HAEM89-007

Term	Definition
SAE	Serious adverse event
SAP	Statistical analysis plan
SmPC	Summary of Product Characteristics
Sobi	Swedish Orphan Biovitrum AB (publ)
SUSAR	Suspected unexpected serious adverse reaction
Target joint	Three or more spontaneous bleeds into a single joint within a consecutive 6-month period. Where there have been ≤ 2 bleeds into the joint within a consecutive 12-month period the joint is no longer considered a target joint (1) Recurrence is defined as ≥ 3 spontaneous bleeds in a single joint within any consecutive 6-month period after target joint resolution.
US	Ultrasound

3 Ethics

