5.2.1 Secondary endpoints supporting the secondary objective(s)

- Change from baseline in HEAD-US score for hypertrophic synovium at 6, 12 and 18 months
- Change from baseline in HEAD-US score for cartilage at 6, 12 and 18 months
- Change from baseline in HEAD-US score for bone at 6, 12 and 18 months
- Change from baseline in total HJHS at month 18 (EOS)
- Number and location of target joints at baseline, 6, 12 and 18 months
- Total Annualized bleeding rate (ABR), joint ABR, target joint ABR, traumatic/spontaneous ABR
- Patient-Reported Outcomes Measurement Information System (PROMIS) physical function/activity scores at baseline and 18 months
- PROMIS pain intensity and interference scores at baseline and 18 months
- International Physical Activity Questionnaire - Short Form (IPAQ-SF) scores at baseline and 18 months

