6.1 Overall study design and plan

This is a prospective, low-interventional, single-arm, multicentre study to describe the joint health over an 18-month period of prophylactic treatment with rFVIIIFc or rFIXFc in patients with haemophilia A or haemophilia B in a real-world setting. Approximately 250 patients will be enrolled in the study. Around 80% of the patients are expected to have haemophilia A and around 20% haemophilia B.

Retrospective data from patient medical records will be collected for at least 6 months before enrolment in the study. From enrolment and throughout the study, patients will perform on-site study visits at 6-month intervals. Each patient is expected to actively participate in the study for 18 months (from baseline to end of study [EOS] visit).

Joint health will be assessed with HEAD-US and HJHS scoring. Quality of life and physical activity will be assessed with PROs. Patients will be on prophylactic treatment with rFVIIIFc or rFIXFc according to usual clinical practice and the dosing guide in the respective Summary of Product Characteristics (SmPC). Choice of treatment will not be dictated by the study protocol.

The recruitment period is planned to be approximately 12 months from the timepoint when the first patient is enrolled in the study. Around 60 sites in approximately 11 European countries are expected to participate in the study.

No specific evaluation committees will be utilized for this study, since it is a low-interventional study having no interventions posing more than minimal risk to the patients.

Interim analyses are planned to be performed during the study. The first interim analysis is to be performed once recruitment is completed. The purpose of the first interim analysis is to assess the baseline variability of HEAD-US score results and to share baseline characteristics with the haemophilia community. The second interim analysis is planned to be performed once at least 50% of the patients have completed their 12-month visit and will evaluate the joint health status at that time.

In an optional, exploratory sub-study, data will be collected via the florio HAEMO app. All exploratory endpoints and objectives in the study are related to the exploratory sub-study.

[figure not shown]
The overall study design is described in Figure 1.

Sobi

Eftrenonacog alfa/Alprolix® - Efmorocog alfa/Elocta®

Clinical Study No: Sobi.HAEM89-007

Figure 1 Study Design

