6.5.3 Haemophilia history

Haemophilia history will be collected at the baseline/enrolment visit including the following:

- severity of disease
- type of haemophilia
- age at diagnosis
- inhibitor history
- type of prophylactic treatment (primary, secondary or tertiary prophylaxis)
- age at prophylaxis initiation
- haemophilia prescription information (product, regimen, and dosing) from the 6 months period prior to enrolment
- haemophilia prescription information (product, regimen, and dosing) at time of enrolment
- previous non-factor therapy (product, start and stop date)
- bleeding episodes (location, spontaneous/traumatic) from the 6 months prior to enrolment
- date of first injection with rFVIIIFc or rFIXFc

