6.5.6 Target and impaired joints

At baseline, information on target joints (presence and location) will be recorded as per the assessment of the investigator. For the follow-up visits, resolution/reccurence/development of target joints will be calculated based on the investigator reported bleeds, as per the target joint definitions for resolution, recurrence and development (1).

Information on the presence, location and related assessments of impaired joints will be recorded as per the assessment of the investigator. A joint can simultaneously be a target joint and an impaired joint. The status of an impaired joint will be assessed at the baseline visit, and details on clinical/functional investigations performed as well as any changes in e.g. pain will be collected.

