8.3.4 Analysis related to secondary objectives

A detailed description of the secondary objectives and endpoints are found in section 5.2 of the protocol. The secondary endpoints will be based on both the FAS and the PP set.

HEAD-US scores (hypertrophic synovium, cartilage, bone) and HJHS scores (Sum of joint totals, Global Gait Score, HJHS total score) will be presented using descriptive statistics at each visit. In addition, the change from baseline to each post-baseline visit will also be presented with descriptive statistics and the estimated average change from baseline together with 95% CI.

The number and proportion of patients with target joints as well as the total number of target joints will be analyzed by summary statistics as well as frequency tables for each visit. Target joint locations will be given for each visit in frequency tables.

The ABR for treated bleeds and ABR for all (treated and untreated bleeds) will be derived for the period between baseline and month 6 visit, for the period between month 6 and month 12 visit, for the period between month 12 and month 18, and as well as for the entire 18-month study period. The ABR will also be presented for the retrospective 6 month period. ABR will be presented using summary statistics for all periods and also be presented by type (spontaneous/traumatic/unknown) and location (joint/muscle/unknown). The number and

Sobi

Eftrenonacog alfa/Alprolix® - Efmorocog alfa/Elocta®

Clinical Study No: Sobi.HAEM89-007

percentage of patients who had at least one bleeding episode (overall, circumstance, locations and target joint) over the 18-month prospective period will also be presented as well as the corresponding total number of episodes. The number and proportion of patients with 0 joint bleeds will be presented, as well as the number and proportions with 1, 2 etc. joint bleeds. To justify an estimation of the ABR and to reduce potential misclassification, a patient had to be documented for at least 3 months.

PROMIS and IPAQ-SF scores will be presented at baseline and 18 months graphically and in tabular form with descriptive statistics (mean IPAQ-SF score measured as MET-minutes/week) and change.

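### Target-joint status is judged by the investigator at baseline and calculated from bleeds afterwards, so the baseline-to-month-6 step mixes a change of method with real change

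*Combined protocol and SAP*

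**What the plan says.** Section 2.1 makes a joint a target joint after "Three or more spontaneous bleeds into a single joint within a consecutive 6-month period". It ends that status by a longer rule: "Where there have been ≤ 2 bleeds into the joint within a consecutive 12-month period the joint is no longer considered a target joint". The first rule counts spontaneous bleeds only; the second, as worded, counts all bleeds.

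Section 6.5.6 uses two sources of status. For the start of the study: "At baseline, information on target joints (presence and location) will be recorded as per the assessment of the investigator". Afterwards: "For the follow-up visits, resolution/reccurence/development of target joints will be calculated based on the investigator reported bleeds". The schedule of events agrees, marking direct recording of target joints at enrolment and baseline only.

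The secondary endpoint in 5.2.1 nevertheless puts both on one time axis: "Number and location of target joints at baseline, 6, 12 and 18 months". Section 8.3.4 then plans, for each visit: "The number and proportion of patients with target joints as well as the total number of target joints will be analyzed by summary statistics".

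Pre-baseline bleed data exist. Section 6.5.3 collects "bleeding episodes (location, spontaneous/traumatic) from the 6 months prior to enrolment", and 6.1 adds: "Retrospective data from patient medical records will be collected for at least 6 months before enrolment in the study".

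**The concern.** The plan does not give the look-back for the investigator's baseline judgement. It does not say that baseline status will be re-derived by the follow-up algorithm, or whether the 12-month resolution period may include time before baseline. The first step of the series therefore carries a change of method, and how the count behaves at month 6 depends on an unstated choice of window.

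Whether target joints are present, resolve, recur or newly appear is a secondary objective (5.2). The study has no control group (6.2), so the pattern over visits is itself the result. A fall or rise between baseline and month 6 could be read as an effect of prophylaxis when part of it comes from the switch of source.

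**Working it through.** The plan gives no rate, precision or sample-size figure for target joints, so there is none to reproduce. The check applies the two rules of 2.1 to the data available at each visit.

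**Inputs from the documents:** at least 3 spontaneous bleeds in 6 months to qualify; at most 2 bleeds in 12 months to resolve; 6 months of retrospective bleeds; a ±28-day window at months 6 and 12.

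**Assumptions:** 6 months = 182.5 days and 12 months = 365 days; baseline coincides with enrolment (section 6.5.1.2 allows up to 28 days between them); Poisson bleeding at λ = 0.5 to 4 per joint per year, with all bleeds counted as spontaneous. The documents give no bleed rates.

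**1. Only on-study time counts.** The latest month-6 visit has 182.5 + 28 = 210.5 days, short of 365, so no joint can resolve. Month-12 visits fall between days 337 and 393 (365 ± 28), so those before day 365 are also short.

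**2. Retrospective bleeds count; joint qualified in the 6 months before baseline.** For a visit u days after the nominal month-6 date, the 12-month period starts at day (182.5 + u) − 365 = −182.5 + u. For u ≤ 0 every qualifying bleed is still inside, so the probability of resolution is 0. For u > 0, with exactly 3 qualifying bleeds spread evenly over the look-back and none on study:

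P(resolved) = 1 − (1 − u/182.5)³

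This gives 11% at u = 7, 21% at u = 14 and 39% at u = 28, or 10% averaged over visits spread evenly across ±28 days. With on-study bleeding added (400,000 simulated joints), the average is 8%, 6%, 4% and 1% at λ = 0.5, 1, 2 and 4.

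**3. Retrospective bleeds count; joint recorded on older history.** Six retrospective plus six on-study months fill the period, so P(resolved at month 6) = e^(−λ)(1 + λ + λ²/2).

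**4. Meeting the qualifying rule within one 6-month interval.** With m = λ/2, P = 1 − e^(−m)(1 + m + m²/2). This needs only 6 months of data, so new target joints can be added at month 6 under every reading.

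| λ per joint-year | Step 3: at most 2 bleeds in 12 months | Step 4: at least 3 bleeds in 6 months |
|---|---|---|
| 0.5 | 98.6% | 0.2% |
| 1 | 92.0% | 1.4% |
| 2 | 67.7% | 8.0% |
| 3 | 42.3% | 19.1% |
| 4 | 23.8% | 32.3% |

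The step 3 column also gives resolution over 12 fully on-study months, that is, at a month-12 visit on day 365.

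**5. Combining steps 2 and 3.** If a share p of baseline target joints rests on older history, the share resolving at the nominal month-6 date is p × the step 3 figure. At λ = 1 it runs from 0% (p = 0) to 92% (p = 1). The documents do not give p.

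**6. Data coverage when retrospective bleeds count.** With exactly 6 retrospective months, month 6 has between 182.5 + 154.5 = 337 and 182.5 + 210.5 = 393 days, so early visits fall short of 365. Month 12 has at least 182.5 + 337 = 519.5 days, so every in-window visit qualifies.

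**The case against.** Four points on the other side have force.

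- Section 2.1 gives a numerical definition, unlike that of an impaired joint, which rests on clinical relevance. Investigators who apply it may agree with the calculation. That is possible, but 6.5.6 neither requires it nor fixes a look-back.
- The delay in resolution belongs to the cited definition. A joint with three bleeds in the past 12 months is still a target joint, and a month-6 count that says so is correct. This stands.
- The investigator's baseline record is needed, because a 6-month look-back cannot find target joints acquired earlier. This stands too.
- The endpoint is secondary and descriptive with no hypothesis testing, and 8.3.1 leaves detail to a further SAP. This limits the weight of the point. It does not remove it, because the two sources of status are a stated rule and not an omitted detail.

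A reader might infer something stronger: that resolution is almost impossible by month 6, so the count can rise but hardly fall, and then drops at month 12. The documents do not support that. Section 2.1 does not restrict the 12 months to study time, and inclusion criterion 5 admits patients already on the study products, so target joints carried on older history are possible and could leave the count at month 6. A large drop at month 12 is no more certain: 12-month resolution is 92% or more at up to 1 bleed per joint-year, but 68% at 2 and 24% at 4.

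**Conclusion.** The concern holds in a limited form. Baseline and follow-up status come from different methods and are tabulated as one series, so the baseline-to-month-6 difference cannot be read as change in the joints alone.

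Resolution at the nominal month-6 date is 0% if only on-study time counts, and 0% for joints that qualified in the 6 months before baseline. It can be 99%, 92% or 68% (λ = 0.5, 1, 2) for joints on older history if retrospective bleeds count. The zeros follow from the definition and the dates; the other percentages rest on assumed Poisson rates. Because neither the counting rule nor the mix of joint histories is stated, neither the direction nor the net size of the distortion can be derived from the documents.

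The plan should be changed, but this is not critical: the endpoint is secondary and descriptive, and the primary HEAD-US analysis is untouched.

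**What to change.** In 8.3.4, or in the SAP that details it:

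1. Keep the month-6 counts, which are part of a stated endpoint, and keep the investigator's baseline status.
2. Add a like-for-like series that applies the rule of 3 spontaneous bleeds in 6 months to the retrospective 6 months and to each on-study 6-month interval. Show the calculated baseline beside the investigator's.
3. State that the 12-month resolution period may include the retrospective bleeds.
4. Report resolution at each visit only among joints with 12 months of bleed data, retrospective plus on-study. By step 6 of the working this removes some early month-6 visits but no in-window month-12 visit.
5. Show joints that qualified in the look-back separately, and read them for resolution from month 12.

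The cost is wording and a little extra tabulation, since the bleeds are already collected with location and cause. The 6-month look-back cannot re-derive target joints acquired earlier, so both baseline columns are needed. Fixed 6-month intervals will also miss clusters of bleeds that straddle a visit, so the new series supplements the planned counts and does not replace them.
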